Study drug dosage and administration method: Duloxetine (20-mg capsules) is administered orally, once daily after breakfast, for 7 weeks, this consisting of a 6-week treatment period and a 1-week tapering period. During the treatment period, administration is initiated at 20 mg/day, and increased to 40 mg/day at Visit 3, 1 week later. From Visit 4, 1 week after Visit 3, if the CGI-S score is 3 or higher, and there are no concerns about safety, the dose is increased to 60 mg/day. In addition, from Visit 5, after the dose has been temporarily increased to 60 mg/day, if there are safety-related problems, it can be reduced again to 40 mg/day. If the CGI-S score is ≥ 3 , and there are no safety-related problems, after confirming the subject's clinical condition and safety, the dose can be increased again. When the dose is to be increased from 20 to 40 mg/day, or from 40 to 60 mg/day for the first time, the pre-increase dose must be administered for at least 7 days. During the 1-week tapering period, if the duloxetine dose at discontinuation or completion of the treatment period was 60 mg/day, 40 mg/day is administered for the first 3 days of the week, and 20 mg/day is administered for the remaining 4 days. On the other hand, if the dose at discontinuation or completion was 40 mg/day, 20 mg/day is administered for the entire week.

Control drug dosage and administration method: Placebo for 20-mg duloxetine capsules is administered orally, once daily after breakfast, for 7 weeks, this consisting of a 6-week treatment period and a 1-week tapering period as is the administration way in active drug.

Administration period: 7 weeks (6-week treatment period and 1-week tapering period)

Prohibited drugs and therapies: Use of the below drugs, or over-the-counter drugs with equivalent effects, is prohibited from Visit 1 through Visit 9. (completion of the tapering period).

Prohibited drugs that may affect therapeutic evaluation:

- 1) Antidepressants
- 2) Anxiolytics
- 3) Soporific agents, other than the “Permitted soporific agents” in Section 6.2.2.
- 4) Antipsychotics
- 5) Antiparkinsonian agents
- 6) Anticonvulsants
- 7) Mood-stabilizers (lithium carbonate, carbamazepine, sodium valproate)
- 8) Psychostimulants
- 9) Adrenal corticosteroids, excluding externally administered agents such as ear drops, nose drops, eye drops, topical skin formulations, and inhaled formulations.
- 10) Interferon formulations

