5.2 Dosage and regimen

Subjects who are formally enrolled after confirmation of eligibility will be randomly allocated to the duloxetine and placebo groups in accordance with the allocation method stipulated in Section 5.4. The two groups are shown in Table 5-1. Oral administration of duloxetine or placebo will be initiated the day after the registration (Visit 2), with administration once daily after breakfast for 7 weeks, in a 6-week treatment period and a 1-week tapering period. Treatments by methods other than the study drug administration are detailed in Section 6. .

Table 5-1. Study drug regimen for each group

Treatment group	Treatment period			Tapering period	
	Week 1	Week 2	Weeks 3 - 6	Week 7	
				First 3 days	Latter 4 days
Duloxetine group	20 mg/day	40 mg/day	40 or 60 ^a mg/day	20 ^b or 40 ^c mg/day	20 mg/day
	One 20-mg LY248686 capsule and one placebo capsule	Two 20-mg LY248686 capsules	Two 20-mg LY248686 capsules or three 20-mg LY248686 capsules	One 20-mg LY248686 capsule or two 20-mg LY248686 capsules	One 20-mg LY248686 capsule
Placebo group	0 mg/day	0 mg/day	0 mg/day	0 mg/day	0 mg/day
	Two 20-mg placebo capsules	Two 20-mg placebo capsule	Two 20-mg placebo capsules or Three 20-mg placebo capsules	One 20-mg placebo capsules or Two 20-mg placebo capsules	One 20-mg placebo capsules

When the dose is to be increased from 20 to 40 mg/day, or from 40 to 60 mg/day for the first time, the pre-increase dose must be administered for at least 7 days.

- When the CGI-S score is ≥ 3 , and there are no concerns about safety. If there are safety-related problems, as judged by the principal investigator, the dose can be reduced to 40 mg/day. If the CGI-S score is ≥ 3 , and there are no safety-related problems, after confirming the subject's clinical condition and safety, the dose can be increased again.
- If the duloxetine dose at discontinuation or completion of the treatment period was 40 mg/day.
- If the duloxetine dose at discontinuation or completion of the treatment period was 60 mg/day.

One of the following measures will be taken if administration is discontinued during the treatment period:

- 1) Discontinuation during week 1 of treatment period: Promptly discontinue administration.
- 2) Discontinuation during week 2 of treatment period: Discontinue after administration of the study drug at 20 mg/day for a tapering period of 7 days.

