## 8. Treatment course and compliance

### 8.1 Compliance

#### 8.1.1 Duration of administration and total dose

The following analyses will be performed with the safety-analysis set:

- 1) Summary statistics for study drug administration duration will be calculated for each treatment group. Administration duration is defined as follows:

Administration duration (days) = (administration completion date) – (administration initiation date) + 1.

In addition, times (days) will be converted to week units, and the distributions in the following categories will be summarized: less than 1 week; 1 to 2 weeks; 2 to 6 weeks; and more than 6 weeks.

- 2) Summary statistics will be calculated for the total dose of study drug in the duloxetine group.
- 3) With the duloxetine group, for the maximum and final doses during the treatment period, distribution in the following categories will be summarized: 20 mg, 40 mg, and 60 mg.

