- 2) For each treatment group, the number of subjects with a given adverse event, the number of cases, and the incidence rate will be determined by adverse event system organ class and preferred term. However, when calculating the number of subjects with a given adverse event and the incidence rate, if the same adverse event occurs more than once with the same subject, these events will be taken to be have affected one subject. Adverse drug reactions will be tabulated similarly.
- 3) With respect to adverse events with an incidence of 2% or more in at least one treatment group, the number of subjects, number of cases, and incidence rate will be calculated for each adverse event preferred term. Adverse drug reactions will be tabulated similarly.
- 4) For each treatment group, the number of subjects and incidence rate will be calculated for each severity and outcome category, by adverse event system organ class and preferred term. If the same adverse event occurs more than once in different categories with the same subject, it will be taken to have occurred once, in the category with the highest of the below priority ranks. Adverse drug reactions will be tabulated similarly.

Priority rank	Survey item category	
	Severity	Outcome
1	Severe	Death
2	Moderate	Recovery with sequelae
3	Mild	No improvement
4		Partial recovery
5		Recovery
6		Unknown

- 5) For each treatment group, the number of subjects and the incidence will be calculated for each onset timing category (weeks 0 to 1; weeks 1 to 2; weeks 2 to 3; weeks 3 to 6; later than week 6) for adverse events during the treatment period, by system organ class and preferred term. The denominator of the incidence rate will be the number of subjects with administration duration no shorter than the lower limit of each onset time category. The onset timing will be calculated as follows:  

$$\text{Onset timing [day]} = (\text{onset date}) - (\text{administration initiation date}) + 1$$
When calculating the number of subjects and the incidence rate, if the same adverse event occurs in different categories more than once in the same subject, it will be taken to have occurred with one subject in each of the relevant categories. Adverse drug reactions will be tabulated similarly.

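### SAP 10.1 item 5: the after-week-6 row of the onset-timing table is near zero by construction, mainly because only events in the 6-week treatment period are counted

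*SAP*

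**What the plan says.** SAP 10.1 item 5 gives the number of subjects and the incidence in the onset categories "weeks 0 to 1; weeks 1 to 2; weeks 2 to 3; weeks 3 to 6; later than week 6". The scope of this table is limited, since it is drawn up "for adverse events during the treatment period, by system organ class and preferred term". Onset day is counted with the first dose as day 1. The item then states: "The denominator of the incidence rate will be the number of subjects with administration duration no shorter than the lower limit" of each category.

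Other places bear on how to read this:

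- SAP 8.1.1 defines "Administration duration (days) = (administration completion date) – (administration initiation date) + 1". It sets no treatment-period limit and does not say which dose marks completion. Item 3 of the same section, and SAP 8.1.2, do name the treatment period where that is the intended span.
- SAP section 2 lists a 6-week treatment period and a separate 1-week tapering period. SAP 10.1 item 6 tabulates taper events on their own.
- The protocol synopsis and Protocol 5.2 give 7 weeks of administration, made up of 6 weeks of treatment and 1 week of taper.
- SAP Appendix 2 and Protocol Table 7-3 place Visit 8 on day 42, with a window of −3 to +1 days.
- Protocol 8.11.1 asks for treatment-emergent events to be summarized by onset timing. Protocol 7.6.7.11 defines these as any event with onset after the first dose, and Protocol 7.6.7.2 collects events to 7 days after the last dose.
- Protocol 8.1 requires the SAP to give the reason for any change to the planned analysis.

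**The concern.** Numerator and denominator of the last category appear to cover different time spans. Events must fall in a treatment period that is all but over by day 42. Subjects are counted as at risk by a duration that seems to run through the taper.

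The resulting row would suggest that adverse events almost stop after week 6, which is when the dose is being tapered. Protocol 3.1 gives limiting discontinuation events as the purpose of the taper. On the literal text, events in the follow-up week appear in neither item 5 nor item 6, so no table by timing shows them. The restriction to the treatment period is also narrower than Protocol 8.11.1, and the SAP gives no reason for it.

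**Working it through.** **Inputs.** First dose is the day after Visit 2 (Protocol 5.2), so with Visit 2 as day 0 the onset day equals the study day. Visit 8 falls on days 39–43 (SAP Appendix 2). The taper is 7 days, for completers and for withdrawals from week 2 on (Protocol 3.1, 5.2). Group size is 74 and dropout 10% (SAP 4.3). I take the last category as onset day 43 or later, with a lower limit of 42 days.

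**The plan's own figure.** 42 + 7 = 49 days = 7 weeks, which matches the protocol's administration period.

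**Eligible time in the last category, completers taking the full taper.**

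| Visit 8 on day | Treatment-period days after day 42 | Total administration days | In the ≥42-day denominator |
|---|---|---|---|
| 39 | 0 | 46 | yes |
| 40 | 0 | 47 | yes |
| 41 | 0 | 48 | yes |
| 42 | 0 | 49 | yes |
| 43 | 1 | 50 | yes |

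A withdrawal on day 35 or later who tapers is also in the denominator (35 + 7 = 42).

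**Size of the denominator.** Completers: 74 × 0.9 = 66.6. Withdrawals: 7.4, assumed to be spread evenly over 42 days. Last category: 66.6 + 7.4 × 8/42 = 68.0.

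**Expected any-event rate in the last category.** The documents give no event risk, so I assume a 6-week risk R of 30%, 50% or 70% and a constant hazard h = −ln(1 − R)/42. The one-day risk is 1 − exp(−h). If a share f of completers have Visit 8 on day 43, the rate is 66.6 × f × (1 − exp(−h)) / 68.0. For R = 50% and f = 1: h = 0.0165, the one-day risk is 1.64%, and 66.6 × 0.0164 / 68.0 = 1.60%. If events over k further days counted, the rate would be 1 − exp(−kh).

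| | R = 30% | R = 50% | R = 70% |
|---|---|---|---|
| Literal text, no Visit 8 on day 43 | 0% | 0% | 0% |
| Literal text, 25% on day 43 | 0.21% | 0.40% | 0.69% |
| Literal text, all on day 43 | 0.83% | 1.60% | 2.77% |
| Events counted through the 7-day taper | 5.8% | 10.9% | 18.2% |
| Events counted through taper and follow-up (14 days) | 11.2% | 20.6% | 33.1% |

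Rates by preferred term would be lower throughout.

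**Which part causes it.** With a denominator limited to treatment-period duration, the last category would still hold at most one day, and only for subjects with Visit 8 on day 43. The numerator limit is therefore the main cause. The taper-inclusive denominator only spreads the few possible events over almost all completers.

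**Earlier categories.** A withdrawal on day 10 who tapers has 10 + 7 = 17 days and is counted in weeks 2 to 3 (17 ≥ 14), although no later event can count. Week-1 withdrawals get no taper, so the subjects wrongly added are:

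- Weeks 2 to 3 (limit 14): withdrawals on days 8–13, 7.4 × 6/42 = 1.1. The denominator is 72.8 instead of 71.7, or 1.5% more.
- Weeks 3 to 6 (limit 21): withdrawals on days 14–20, 7.4 × 7/42 = 1.2. The denominator is 71.7 instead of 70.5, or 1.7% more.
- Withdrawals on days 21–34 are rightly in weeks 3 to 6 and reach 28–41 days with the taper, below 42. They change no denominator.

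**The case against.** The strongest reply is that item 5 may simply mean treatment-emergent events. Protocol 8.11.1 and the opening of SAP 10.1 have that scope, the SAP announces no change, and Protocol 6.2 once uses the term treatment period for Visit 1 to Visit 10. On that reading the last category and the denominator fit together far better, and an overlap with item 6 would do no harm, since taper events already appear in both items 2 and 6. This reading is possible. It goes against SAP section 2, and against SAP 8.1.1 item 3 and 8.1.2, where the treatment period is named to mark a narrower span. If it is what was meant, item 5 still needs rewording.

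Second, the SAP nowhere says that administration duration includes the taper, and output details are left to separate mock tables. This stands: the inclusion is inferred from the unrestricted formula and the 7-week period. It matters less than it seems, because the last category is nearly empty under either denominator.

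Third, an open-ended last category may serve as overflow for late visits. Protocol 7.8 treats out-of-window data as missing for that visit but does not say treatment ends then, and Protocol 5.6 supplies a spare 7-day book. This also stands: the row is near zero, not exactly zero.

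Fourth, nothing is lost. Taper events have their own table in item 6, and all treatment-emergent events enter items 1 and 2. This is correct and limits the weight of the point.

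**Conclusion.** The point holds for the literal text with Visit 8 in window. The last category offers 0 or 1 eligible day per subject over a denominator of nearly all completers (about 68 of 74 per group). Its any-event rate is then 0% to 2.8% for assumed 6-week risks of 30% to 70%, against 5.8% to 18.2% if events through the taper counted. These rates rest on a constant hazard and on 10% dropout spread evenly. The zero-or-one-day count rests only on the visit window.

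The impact is one descriptive safety table with no test specified for it. Efficacy, the overall adverse event comparison and data collection are untouched.

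Three stronger inferences are not supported:

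- A reader might infer that the taper in the denominator is what empties the row. Correcting the denominator alone would leave it uninformative.
- A reader might infer an understatement of about 10% in earlier categories (74/67 = 1.10). That needs every withdrawal to fall in the same short stretch and to take the taper, which may be omitted under Protocol 5.2. With dropout spread evenly the effect is about 1–2%, in two categories only.
- A reader might infer that completers cannot be told from late withdrawals, because tapered withdrawals from day 36 on share the top duration category of SAP 8.1.1 with them. SAP 7.1 already reports treatment-period completers and withdrawals by group, and taper completers and withdrawals separately, so the exposure table need not be split.

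**What to change.** Choose one of two edits to SAP 10.1 item 5:

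1. Count all treatment-emergent events, as Protocol 8.11.1 asks, and define the denominator over the same time span. If events are counted to 7 days after the last dose, the at-risk time must run to that point too.
2. Keep treatment-period events, base the denominator on treatment-period duration (first dose to last treatment-period dose), delete the category after week 6, and state the reason for departing from Protocol 8.11.1, as Protocol 8.1 requires.

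The first stays closer to the protocol and gives the last category real content. In either case, define the administration completion date in SAP 8.1.1 and say whether it includes the taper.

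The cost is a few lines of SAP text and one derived variable. Protocol 5.9 already has the start and end dates of each dose entered in the CRF, so no new data are needed.

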5.3 Selection of dose and timing of administration for each subject

Subjects will be randomly allocated to the duloxetine and placebo groups. With the duloxetine group, administration will be initiated at 20 mg/day, and increased to 40 mg/day at Visit 3, 1 week later. From Visit 4, 1 week after Visit 3, if the CGI-S score is 3 or higher, and there are no concerns about safety, the dose will be increased to 60 mg/day. In addition, from Visit 5, after the dose has been temporarily increased to 60 mg/day, if there are safety-related problems, it can be reduced again to 40 mg/day. If the CGI-S score is ≥ 3 , and there are no safety-related problems, after confirming the subject's clinical condition and safety, the dose can be increased again. When the dose is to be increased from 20 to 40 mg/day, or from 40 to 60 mg/day for the first time, the pre-increase dose must be administered for at least 7 days. During the 1-week tapering period, if the duloxetine dose at discontinuation or completion of the treatment period was 60 mg/day, 40 mg/day will be administered for the first 3 days of the week, and 20 mg/day will be administered for the remaining 4 days. On the other hand, if the dose at discontinuation or completion was 40 mg/day, 20 mg/day will be administered for the entire week.

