5.9 Treatment compliance

At each study site visit, subjects will bring study drug books (containing unused drug) with them, and will return the books that are no longer needed. However, the 1-week book containing spare study drug will be returned at Visit 8. The investigator or sub-investigator will confirm treatment compliance from the study drug books, ascertaining the exact amount of the drug taken since the previous visit. At each visit, the duration of study drug administration, dosage, reasons for prescription change or continuation, a number of unused capsules will be entered in the CRF. Other items entered in the CRF will be whether prescription has been in accordance with the allocation no. released by the Registration Center, and, if not, the prescribed drug ID, and the study drug administration initiation and completion dates for each dose. If unused study drug is found when checking the treatment compliance, the investigator or sub-investigator will instruct the subject about the importance of treatment compliance.

The subject is taken to be noncompliant when, since the previous visit, the proportion of days on which the drug has not been taken as stipulated exceeds 30%. On the other hand, if the drug taken exceeds the stipulated dose on even one occasion, this is taken to constitute noncompliance, and a Special Situations

Report is submitted to the sponsor.

6. Restrictions on subjects

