- 6) With subjects in the safety analysis set who are transferred to the tapering period, adverse events that occur during the tapering period will be summarized. For each treatment group, the number of subjects with a given adverse event, the number of cases, and the incidence rate will be determined by adverse event system organ class and preferred term. However, when calculating the number of subjects with a given adverse event and the incidence rate, if the same adverse event occurs more than once with the same subject, this event will be taken to be have affected one subject. Adverse drug reactions will be tabulated similarly.

- 7) For each treatment group, with respect to adverse events for which the below standard MedDRA queries (SMQ) are applicable, the number of subjects, number of cases, and incidence rate will be determined by system organ class and preferred term. However, when calculating the number of subjects with a given adverse event, and the incidence rate, if the same adverse event occurs more than once with the same subject, this event will be taken to be have affected one subject.

SMQ	Range
Suicide/self-injury	Broad search
Hostility/aggression	Broad search

- 8) With respect to the duloxetine group, the number of subjects and incidence rate will be calculated for each duloxetine dose category (20 mg, 40 mg, 60 mg) at the adverse event onset date, by system organ class and preferred term. When calculating the number of subjects and the incidence rate, if the same adverse event occurs in different categories more than once in the same subject, it will be taken to have occurred with one subject in each of the relevant categories. Adverse drug reactions will be tabulated similarly.
- 9) Subgroup analyses will be performed for the below demographic factors. For each treatment group, the number of subjects and the incidence rate will be calculated by adverse event system organ class and preferred term.
- Age (<12, ≥12)
  - Sex (male, female)

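### The SAP's adverse-event table by duloxetine dose at onset gives crude incidence with no dose-specific denominator, no time at each dose and no separation of taper days, so its 20, 40 and 60 mg columns cannot be compared

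*SAP*

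**What the plan says.** SAP 10.1 item 8 covers the duloxetine group only. It reports the number of subjects and the incidence rate, by system organ class and preferred term, "for each duloxetine dose category (20 mg, 40 mg, 60 mg) at the adverse event onset date". A subject with the same event at two doses counts once in each. The item gives no denominator. The only general definition, in item 1 of the same section, is a proportion of the subjects in the analysis set. Item 8 is not restricted to the treatment period, and section 10.1 takes in all events from the first dose onwards.

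The regimen is in Protocol 5.2 (Table 5-1) and 5.3. In the duloxetine group "administration will be initiated at 20 mg/day, and increased to 40 mg/day at Visit 3, 1 week later". From Visit 4, "if the CGI-S score is 3 or higher, and there are no concerns about safety, the dose will be increased to 60 mg/day". Before each first increase "the pre-increase dose must be administered for at least 7 days". Dosing runs "in a 6-week treatment period and a 1-week tapering period". After 60 mg the taper is such that "40 mg/day will be administered for the first 3 days of the week, and 20 mg/day will be administered for the remaining 4 days"; alternatively, "if the dose at discontinuation or completion was 40 mg/day, 20 mg/day will be administered for the entire week".

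Two neighbouring items are more careful. Item 5 (onset timing, both arms, treatment period) states an at-risk denominator for each period, and item 6 tabulates taper events on their own. SAP 8.1.1 summarises total duration, total dose, and maximum and final dose, but not time at each dose. Protocol 5.9 puts on the CRF "the study drug administration initiation and completion dates for each dose".

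**The concern.** The chance that a subject has an event while on a given dose grows with the days spent on it. Item 8 sets three proportions side by side although the days behind them differ by design. Nothing in the table, or in the other planned outputs, lets a reader correct for that. The 20 and 40 mg columns also mix days on the way up with days on the way down, and an event after the last dose has no category.

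This is the only planned display of adverse events by dose, in a paediatric trial in which the dose varies between 40 and 60 mg. Some readers will compare its columns. An excess at 60 mg could be no more than longer exposure; a flat or falling pattern could be early events that fell in the titration weeks.

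**Working it through.** The documents state no adverse-event rate by dose, so there is no figure of the plan's to reproduce. The days come from the regimen; the risks and the shares raised are assumptions.

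**Nominal days at 20 / 40 / 60 mg**

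| Subject | Treatment period | With full taper |
|---|---|---|
| Raised at Visit 4, stays on 60 mg | 7 / 7 / 28 | 7+4 = 11 / 7+3 = 10 / 28 |
| Never raised | 7 / 35 / 0 | 7+7 = 14 / 35 / 0 |

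For the raised subject the ratio of time at 60 mg to time at 20 mg is 28/7 = 4.0 without taper and 28/11 = 2.5 with it. Visit windows and later dose changes shift these days.

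**Constant risk, the same at every dose, all subjects raised.** With weekly risk h, expected incidence over d days is 1 − (1 − h)^(d/7). At h = 5%:

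- 7 days: 5.0%
- 10 days: 1 − 0.95^(10/7) = 7.1%
- 11 days: 1 − 0.95^(11/7) = 7.7%
- 28 days: 1 − 0.95^4 = 18.5%

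Without taper the columns read 5.0 / 5.0 / 18.5%, a 60-to-20 ratio of 3.7. With taper they read 7.7 / 7.1 / 18.5%, a ratio of 2.4. For h from 1% to 20% the ratio runs from 3.9 down to 3.0 without taper, and from 2.5 down to 2.0 with it. The pattern is a step at 60 mg, not a steady gradient, because 20 and 40 mg have nearly equal time.

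**Share raised and denominator (h = 5%).** Let f be the share raised.

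- Whole-group denominator, no taper: 60 mg exceeds 20 mg only if f × 18.5% > 5.0%, so f > 27%.
- Whole-group denominator, taper counted: a never-raised subject has 14 days at 20 mg, giving 9.75%. The condition is f × 18.55 > f × 7.74 + (1 − f) × 9.75, so f > 9.75/20.56, about 47%.
- Against 40 mg, a never-raised subject has 35 days, giving 22.6%. The 60 mg column is higher only if f exceeds 22.62/36.17 = 63% (no taper) or 22.62/34.10 = 66% (taper).
- Ever-exposed denominator: the 60-to-20 ratio is 3.7 whatever the share raised without taper, and 2.0 to 2.25 with taper when 25% to 75% are raised.

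**Risk that falls over time.** Take a week-1 risk of 10% (hazard −ln 0.9 = 0.1054), unrelated to dose, with all subjects raised and taper counted.

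- Hazard falling 30% a week: 10.6 / 7.6 / 12.3%, so the excess at 60 mg almost disappears.
- Hazard falling 50% a week: 10.1 / 5.2 / 4.8%, so the pattern reverses.

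**Person-time.** With a constant weekly risk of 5%, first events per 100 person-weeks are −ln(0.95) × 100 = 5.13 at every dose, ratio 1.00. With the hazard falling 30% a week this is no longer so. Cumulative hazard at 20 mg is 0.1054 × (1 + 0.7^6 × 4/7) = 0.1124 over 11/7 weeks, or 7.2 per 100 person-weeks. At 60 mg it is 0.1054 × (0.49 + 0.343 + 0.240 + 0.168) = 0.1308 over 4 weeks, or 3.3 per 100. In the treatment period alone the contrast is 10.5 against 3.3. Person-time corrects for length of exposure, not for when the exposure falls.

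**The case against.** The strongest reply is that the direction of the distortion is not known. Constant risk over seven weeks has no support in the documents; Protocol 7.6.1 asks for special care in the first two weeks, so early events are a real possibility. The step to 60 mg depends on CGI-S and safety, and no share reaching it is stated. A reader might infer that titration to 60 mg is forced and that the table will therefore show a false dose-response of nearly fourfold. The documents support neither. Four to one in time is the maximum, reached only if taper days are left out or the taper is skipped, whereas item 8 as written does not exclude taper events. This part of the objection stands and limits what can be claimed.

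It is also right that events per person-week, used alone, could mislead the other way: when events cluster early they show a falling pattern with dose although risk does not depend on dose. Person-time therefore belongs beside the crude figures and should not replace them.

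Finally, item 8 is descriptive, has no test and concerns one arm, while items 5 and 6 give some help with timing and taper. That keeps the point minor. It does not answer it, because neither item gives time at each dose. That the pattern can go either way on quantities the table does not show is the reason its columns are not comparable.

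**Conclusion.** The point holds as one of non-comparability. Item 8 leaves open the denominator, the time at each dose and the handling of taper and post-dose events. Under constant, dose-independent risk with all subjects raised, crude incidence at 60 mg would be 3.0 to 3.9 times that at 20 mg without taper events, and 2.0 to 2.5 times with them, for assumed weekly risks of 1% to 20%. With fewer subjects raised and a whole-group denominator, or with risk that falls quickly, the artefact shrinks, vanishes or reverses. It should not be stated that the table will show a false dose-response, only that it cannot tell one from unequal exposure. This is a minor, worthwhile improvement to a secondary safety table.

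**What to change.** In SAP 10.1 item 8:

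1. Keep the crude counts, and state that the denominator is subjects ever exposed at that dose.
2. Add person-weeks at each dose and first events per person-week, from the dose start and end dates on the CRF.
3. Limit the main table to the treatment period, since item 6 already covers taper events. This also removes post-dose events that have no dose category.
4. Footnote that dose remains confounded with time on treatment and with selection into 60 mg, and that the table is to be read beside the by-period, by-arm table of item 5.

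The parts belong together. Steps 1 and 3 without step 2 would leave the crude 60-to-20 ratio at 3.7 in the 5% constant-risk example, and step 2 without step 4 would hide the effect of early events.

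The cost is a small programming change and one larger descriptive table. No new data are needed, and the regimen, the primary analysis and the comparison of adverse events with placebo are untouched.
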